3.7.2.3.2 Dyspnea

The presence/absence of dyspnea will be assessed. The date and time, and result of assessment will be recorded in a source document and a CRF.

3.7.2.3.3 Jugular Venous Distension

The presence/absence of jugular venous distension will be visually assessed. The date and time, and result of assessment will be recorded in a source document and a CRF.

3.7.2.3.4 Respiration Rate at Rest

Respiration rate at rest will be measured by auscultation using a stethoscope, or by observing respiratory movement of the thorax (up-and-down movement of the chest) (times/minute). The date and time, and result of measurement will be recorded in a source document and a CRF.

3.7.2.3.5 Pulse Rate

A calibrated measuring instrument should be used to determine pulse rate after resting for at least 3 minutes. The status (measured/not measured), date and time, and result of measurement will be recorded in a source document and a CRF.

3.7.2.4 Chest X-ray (Pulmonary Congestion, Cardiothoracic Ratio, and Pleural Effusion)

A calibrated instrument should be used to perform chest x-ray, and the date of chest x-ray will be recorded in a source document and a CRF. An obtained radiograph will be assessed for pulmonary congestion, cardiothoracic ratio, and pleural effusion as described below, and the result of assessment will be recorded in a source document and a CRF.

3.7.2.4.1 Pulmonary Congestion

The grade of pulmonary congestion will be assessed according to Table 3.7.2.4.1-1, and the date and result of assessment will be recorded in a source document and a CRF.

Table 3.7.2.4.1-1 Criteria for Grading Pulmonary Congestion

	Grade	Criterion
0	None	No congestion
1	Mild	Pulmonary venous congestion
2	Moderate	Interstitial pulmonary edema
3	Severe	Alveolar pulmonary edema

Modified from the criteria by Forrester JS, et al.⁶

3.7.2.4.2 Cardiothoracic Ratio

Cardiothoracic ratio (%) will be measured, and the date and result of measurement will be recorded in a source document and a CRF. For the result of measurement, a value to the first decimal point should be recorded.

3.7.2.4.3 Pleural Effusion

The presence/absence of pleural effusion will be assessed, and the date and result of assessment will be recorded in a source document and a CRF.

3.7.2.5 Central Venous Pressure (Only Subjects With Central Venous Catheterization)

In subjects with central venous catheterization who can undergo measurement before and after tolvaptan administration, a calibrated instrument should be used to determine central venous pressure (mmHg) in the way specified by each trial site. The date and result of measurement will be recorded in a source document and a CRF.

3.7.2.6 Retention of Pericardial Effusion (Only Subjects Requiring Echocardiography)

For subjects who have been found to have excessive retention of pericardial effusion by echocardiography before tolvaptan administration and have undergone echocardiography again after administration, a change in the degree of retention from that before administration (decrease, no change, or increase from that before administration) will be assessed. The date and result of assessment will be recorded in a source document and a CRF. A calibrated instrument should be used for echocardiography.

3.7.3 Safety Assessments

3.7.3.1 Adverse Events

Refer to [Section 5](#).

3.7.3.2 **Laboratory tests**

For laboratory tests, each trial site should use appropriate equipment and apparatuses with reliable precision, and follow the procedures specified by the site (measurement at the site). When measurement at the site is not feasible, samples may be sent to the contract research organization for clinical laboratory tests (hereafter, central laboratory) for measurement. The central laboratory will measure the following items according to the procedures specified by the laboratory, and report the result of measurement to the sponsor, and the investigator or subinvestigator. The status (with or without blood/urine sampling), the date and time of blood sampling, the date of urine sampling, and the result of measurement will be recorded in a source document and a CRF. The result of measurement by the specified central laboratory does not have to be recorded.

The case where the subject cannot provide urine sample for some reason despite having received an instruction to urinate will not be regarded as a deviation, but the reason should be recorded in a CRF. To ensure the safety of the subject, a sample should be obtained at a different time or day.

Unscheduled laboratory tests, if required at the occurrence of AEs or for the follow-up of AEs, should be performed at each trial site.

Table 3.7.3.2-1 Clinical Laboratory Assessments

Hematology: Hemoglobin Mean Corpuscular Hemoglobin Concentration Mean Corpuscular Volume Hematocrit Red Blood Cell count White Blood Cell count with differential Platelet count	Serum Chemistry: Alkaline Phosphatase ALT AST Bilirubin, total Blood Urea Nitrogen Uric acid Cholesterol Creatinine Gamma Glutamyl Transpeptidase Glucose Lactic Dehydrogenase Potassium Protein, total Albumin Sodium Triglycerides
Urinalysis: Color Occult blood Glucose pH Protein Specific gravity	Additional Tests: Urine pregnancy test for all female subjects who have begun menstruation

In all female subjects who have begun menstruation, a pregnancy test will be conducted at screening examination, and results must be available prior to tolvaptan administration.

3.7.3.3 Vital signs

3.7.3.3.1 Body Temperature

A calibrated thermometer should be used to determine body temperature. The status (measured/not measured), date and time, and result of measurement will be recorded in a source document and a CRF. For the result of measurement, a value to the first decimal point should be recorded. The result should be rounded to one decimal place.

3.7.3.3.2 Blood Pressure and Pulse Rate

A calibrated measuring instrument should be used to determine blood pressure (systolic and diastolic) and pulse rate after resting for at least 3 minutes. The status (measured/not measured), date and time, and result of measurement will be recorded in a source document and a CRF.

3.7.3.4 12-lead Electrocardiogram

A 12-lead ECG monitors sent by a central ECG measurement facility should be used to obtain an ECG according to the procedure specified by the laboratory. Based on the obtained ECG, the investigator or subinvestigator will record the status (measured/not measured) and date of 12-lead ECG measurement, and the result of assessment (normal or abnormal) in a source document and a CRF. An abnormal finding should be described in the source document and the CRF. The ECG will be sent to the central ECG measurement facility to measure heart rate, and PR, RR, QRS, QT, and QTc (QTcB, QTcF) intervals. The measurement report for the ECG will be sent to the investigator or subinvestigator, and the sponsor. The investigator or subinvestigator will refer to the measurement report to review the result of 12-lead ECG assessment, and sign and date the measurement report. For the measurement report, an electronic file submitted to the sponsor by the central ECG measurement facility is regarded as a source document, and the entry of the result in the CRF is unnecessary.

3.7.3.5 Pregnancy Test

1) Subjects

All female subjects who have begun menstruation at the time of pregnancy test will undergo the pregnancy test. Subjects with a history of hysterectomy or bilateral ovariectomy are regarded as women of nonchild-bearing potential, and do not have to undergo the pregnancy test.

2) Procedure

Each trial site should use a pregnancy test reagent provided by the sponsor to perform urine hCG test in female subjects of child-bearing potential (see [Section 5.5](#)). If the result of test unclear, urine hCG test should be repeated. The investigator or subinvestigator will review the result of test, and record the status, date, and result (positive or negative) of test in a source document and a CRF. For a subject who is urine hCG test positive and suspected to be pregnant by the investigator or subinvestigator, treatment should be discontinued according to the rules specified in [Section 5.5](#).

3.7.4 Pharmacokinetic/Pharmacodynamic Assessments

3.7.4.1 Pharmacokinetic Assessments

3.7.4.1.1 Pharmacokinetic Blood Samples

- 1) Time points of blood sampling (see [Section 3.7.1.5](#) for time points in treatment at reduced dose)

Before administration, and 2 to 4, 10 to 14, and approximately 24 hours after administration on the third day of treatment with tolvaptan at 0.05, 0.15, 0.3, or 0.5 mg/kg/day.

- 2) Procedures for blood sampling and measurement

At time points shown in [Section 3.7.4.1.1 1](#)) and Table 3.7-1, a pharmacokinetic blood sample will be collected in a blood-collecting tube containing heparin sodium through an indwelling catheter or direct venipuncture. Cases where the subject cannot provide a blood sample for some reason will not be regarded as a deviation. The status (collected/not collected), and exact date and time of collecting a pharmacokinetic blood sample will be recorded in a CRF.

All samples will be shipped to the bioanalytical laboratory shown in Appendix 1 to determine the plasma concentrations of OPC-41061 (tolvaptan), DM-4103, and DM-4107 according to an established procedure. Detailed handling and shipping instructions are provided in Appendix 1.

- 3) Rationale for the time points of blood sampling

To determine the pharmacokinetics of tolvaptan in pediatric heart failure patients, data on the plasma concentrations of OPC-41061 and its metabolites (DM-4103 and DM-4107) will be collected. For the time points of blood sampling, a trial in adult CHF patients (Trial 156-06-004) was referred to. As a result of consideration, a total of 4 time points (before administration, at around peak time [2-4 hours after

administration], and at times in an elimination phase [10-14 hours and 24 hours after administration]) are set so that the pharmacokinetic parameters of OPC-41061 can be determined by population pharmacokinetic analysis which will be separately conducted.

3.7.4.2 Pharmacodynamic Assessments

3.7.4.2.1 Daily fluid intake

At the same interval as that for measurement of daily urine volume, daily fluid intake (beverages [eg, juice, milk, tea], water, and transfusion, etc) will be determined. During the pretreatment observation period, daily fluid intake will be measured for the time interval starting at an instruction to urinate after breakfast and ending at complete urination immediately before administration on the following day. After start of tolvaptan administration on the first day of the treatment period, daily fluid intake will be determined for each time interval from the point after complete urination immediately before administration of the day to the point after complete urination immediately before administration on the following day.

The status (measured/not measured), start date and time, and completion date and time of measurement, as well as daily fluid intake will be recorded in a source document and a CRF. Water the subject drinks with tolvaptan will be included in the fluid intake after administration.

3.7.4.2.2 Daily Fluid Balance

Daily fluid balance will be calculated by subtracting “daily urine volume” from “daily fluid intake”. Daily fluid balance will be calculated by the sponsor, and the entry of daily fluid balance in a CRF is unnecessary.

3.7.4.2.3 Serum Osmolality

For laboratory tests, each trial site should use appropriate equipment and apparatuses with reliable precision, and follow the procedures specified by the site (measurement at the site). When measurement at the site is not feasible, samples may be sent to the specified central laboratory for measurement. The central laboratory will perform measurement according to the procedures specified by the laboratory, and report the result of measurement to the sponsor and the investigator or subinvestigator. Serum osmolality does not necessarily have to be measured if its measurement is difficult due to the volume of collected blood or other problems. The status (collected/not collected) and date of blood sampling, and the result of measurement will be recorded in a source

document and a CRF. The result of measurement by the specified central laboratory does not have to be recorded.

3.7.4.2.4 Serum or Blood Sodium Concentration

For laboratory tests, each trial site should use appropriate equipment and apparatuses with reliable precision, and follow the procedures specified by the site (measurement at the site). When measurement at the site is not feasible, samples may be sent to the specified central laboratory for measurement. In that case, however, the same measurement procedure should be followed for each subject. The status (collected/not collected), and date and time of blood sampling, as well as the result of measurement will be recorded in a source document and a CRF. The result of measurement by the specified central laboratory does not have to be recorded.

3.7.4.2.5 Serum or Blood Potassium Concentration

For laboratory tests, each trial site should use appropriate equipment and apparatuses with reliable precision, and follow the procedures specified by the site (measurement at the site). When measurement at the site is not feasible, samples may be sent to the specified central laboratory for measurement. In that case, however, the same measurement procedure should be followed for each subject. The status (collected/not collected), and date and time of blood sampling, as well as the result of measurement will be recorded in a source document and a CRF. The result of measurement by the specified central laboratory does not have to be recorded.

3.7.4.2.6 Urine Osmolality

- 1) Urine sample processing (pretreatment observation period and treatment period)
Approximately 5 mL aliquot of cumulative urine sample will be taken into a sample stock tube and stored in a refrigerator as needed. The date of sampling will be recorded in a source document. Daily urine volume should be determined before taking the aliquot. If spot urine sample has been obtained from a diapered subject, approximately 5 mL aliquot of the spot urine sample will be taken into a sample stock tube. For spot urine sample, urine volume at the interval of urine collection that the spot urine sample has been obtained, as well as the start and completion times of urine collection, will be recorded in a source document.

Cases where the subject cannot provide a urine sample for some reason despite having received the instruction to urinate will not be regarded as a deviation, but the reason should be recorded in a CRF.

2) Measurement

For laboratory tests, each trial site should use appropriate equipment and apparatuses with reliable precision, and follow the procedures specified by the site (measurement at the site). When measurement at the site is not feasible, samples may be sent to the specified central laboratory for measurement. The central laboratory will perform measurement according to the procedures specified by the laboratory, and report the result of measurement to the sponsor and the investigator or subinvestigator. The status (collected/not collected) and date of urine sampling, and the result of measurement will be recorded in a source document and a CRF. The result of measurement by the specified central laboratory does not have to be recorded.

3.7.4.2.7 Daily Urine Sodium Excretion

1) Urine sample processing

Approximately 5 mL aliquot of cumulative urine sample will be taken into a sample stock tube. The date of sampling will be recorded in a source document. Daily urine volume should be determined before taking the aliquot. If spot urine sample has been obtained from a diapered subject, approximately 5 mL aliquot of the spot urine sample will be taken into a sample stock tube. For spot urine sample, urine volume at the interval of urine collection that the spot urine sample has been obtained, as well as the start and completion times of urine collection, will be recorded in a source document.

Cases where the subject cannot provide a urine sample for some reason despite having received the instruction to urinate will not be regarded as a deviation, but the reason should be recorded in a CRF.

2) Measurement of urine sodium concentration

For laboratory tests, each trial site should use appropriate equipment and apparatuses with reliable precision, and follow the procedures specified by the site (measurement at the site). When measurement at the site is not feasible, samples may be sent to the specified central laboratory for measurement. The central laboratory will perform measurement according to the procedures specified by the laboratory, and report the result of measurement to the sponsor and the investigator or subinvestigator. The status (collected/not collected) and date of urine sampling, and the result of measurement will be recorded in a source document and a CRF. The result of measurement by the specified central laboratory does not have to be recorded.

3) Calculation of urinary excretion

Daily urinary excretion will be calculated by multiplying urinary concentration by daily urine volume. Urinary excretion will be calculated by the sponsor, and the entry of urinary excretion in a CRF is unnecessary.

3.7.4.2.8 Daily Urine Potassium Excretion

1) Urine sample processing

Approximately 5 mL aliquot of cumulative urine sample will be taken into a sample stock tube. The date of sampling will be recorded in a source document. Daily urine volume should be determined before taking the aliquot. If spot urine sample has been obtained from a diapered subject, approximately 5 mL aliquot of the spot urine sample will be taken into a sample stock tube. For spot urine sample, urine volume at the interval of urine collection that the spot urine sample has been obtained, as well as the start and completion times of urine collection, will be recorded in a source document.

Cases where the subject cannot provide a urine sample for some reason despite having received the instruction to urinate will not be regarded as a deviation, but the reason should be recorded in a CRF.

2) Measurement of urine potassium concentration

For laboratory tests, each trial site should use appropriate equipment and apparatuses with reliable precision, and follow the procedures specified by the site (measurement at the site). When measurement at the site is not feasible, samples may be sent to the specified central laboratory for measurement. The central laboratory will perform measurement according to the procedures specified by the laboratory, and report the result of measurement to the sponsor and the investigator or subinvestigator. The status (collected/not collected) and date of urine sampling, and the result of measurement will be recorded in a source document and a CRF. The result of measurement by the specified central laboratory does not have to be recorded.

3) Calculation of urinary excretion

Daily urinary excretion will be calculated by multiplying urinary concentration by daily urine volume. Urinary excretion will be calculated by the sponsor, and the entry of urinary excretion in a CRF is unnecessary.

3.7.4.2.9 Plasma AVP Concentration

Blood sample for measurement of plasma AVP concentration will be obtained, and the date of blood sampling will be recorded in a source document for the subject from whom

the sample is available. The sample will be shipped to the specified central laboratory for central measurement. The central laboratory will measure the above item according to the procedure specified by the laboratory, and report the result of measurement to the sponsor and the investigator or subinvestigator. The status (collected/not collected) and date of blood sampling, and the result of measurement will be recorded in a CRF. The result of measurement by the specified central laboratory does not have to be recorded.

3.7.5 End of Trial

The end of trial date is defined as the date on which the last subject completes the trial.

3.8 Stopping Rules, Withdrawal Criteria, and Procedures

3.8.1 Entire Trial

If the sponsor terminates or suspends the trial for any reason, prompt notification will be given to the heads of the trial sites and regulatory authorities in accordance with regulatory requirements.

3.8.2 Individual Site Discontinuation

Individual trial site participation may be discontinued by the sponsor, the investigator, or the IRB if judged to be necessary for medical, safety, regulatory, ethical or other reasons consistent with applicable laws, regulations, and GCP. The head of the trial site will notify the sponsor promptly if the trial is terminated by the investigator or the IRB at the site.

3.8.3 Individual Subject Discontinuation

3.8.3.1 Treatment Discontinuation

Treatment with the IMP should be discontinued, and the withdrawal examination specified in [Section 3.7.1.6](#) should be performed, in the cases listed below. Each investigator or subinvestigator will comprehensively review the circumstances and record the date and reason of discontinuation in a source document and a CRF.

- 1) Legal representative or subject requests to be withdrawn
- 2) After start of IMP administration, a deviation from the inclusion or exclusion criteria is discovered for the subject
- 3) Continuation of treatment is deemed unfeasible due to the occurrence of AEs
- 4) Any of the prohibited concomitant medications are used
- 5) The dose and regimen of restricted concomitant medication were changed within 24 hours before and after start of IMP administration

- 6) Excessive aquaresis is observed, or dose reduction to ≥ 2 dose steps lower is required due to concerns regarding the safety of the subject
- 7) Liver function test value (AST or ALT) increased by ≥ 3 times the upper limit of the reference range for the subject's age and gender
- 8) Serum or blood sodium concentration increased by ≥ 12 mEq/L from that immediately before IMP administration, within 24 hours after administration
- 9) Serum or blood sodium concentration increased by ≥ 8 mEq/L from that immediately before IMP administration, within 8 to 12 hours after administration
- 10) Serum or blood sodium concentration exceeding 145 mEq/L is observed during the treatment period
- 11) Serum or blood potassium concentration exceeds the upper limit of the reference range for the subject's age and gender during the treatment period
- 12) Subject's pregnancy is confirmed or suspected
- 13) The investigator or subinvestigator judges that withdrawal is necessary for any other reasons

After start of treatment with the IMP, a subject may stop treatment permanently for a variety of reasons. Treatment discontinuations may be initiated by a subject who is not satisfied with treatment, when medically necessary due to AEs, when requiring treatment with a disallowed medication or therapy, or other issues, as determined by the investigator. However, options for continued treatment should be offered to the legal representative or subject to the degree possible as described in [Section 3.8.3.4](#).

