3.2 Trial Treatments

3.2.1 Dose and Regimen

Subjects will take tolvaptan 1% granules or tolvaptan 15 mg tablet with water once daily after breakfast.

The initial dose of tolvaptan will be 0.05 mg/kg/day. From the second day of the treatment period and onward, if necessary the dose may be increased to 0.15, 0.3, or 0.5 mg/kg/day according to the rules specified in [Section 3.2.2](#), and then the dose decided for each individual subject will be administered for 3 days. The dose of tolvaptan 1% granules to be administered will be determined depending on the subject's body weight on the day before start of tolvaptan administration; however, the maximum dose is 15 mg/day even if the calculated dose exceeds 15 mg/day. For administration at the maximum dose of 15 mg, tolvaptan 15-mg tablet may be administered in place of tolvaptan 1% granules. If the investigator or subinvestigator judges that there are an excessive aquaresis or safety concerns of subjects, the dose may be reduced (see [Section 3.2.3](#)). For subjects who need to continue treatment after 3-day administration at the dose decided individually, extended treatment for up to 4 days is allowed if the aim is to collect data on administration for up to 7 days and if the investigator or subinvestigator considers the safety of subjects to be ensured (including ensuring safety by dose reduction) (see [Section 3.2.4](#)). The dose, the date and time of administration, and the reason for dose reduction (for dose reduction, see [Section 3.2.3](#)) will be recorded in a source document and a case report form (CRF).

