3.2.3 Reducing the Dose of Tolvaptan

If symptoms associated with excessive aquaresis such as persistent sensation of thirst, dehydration, and hypernatremia are observed or there are safety concerns in subjects, at a discretion of the investigator or subinvestigator, the dose may be reduced only to the next lower dose. In that case, however, the dose of conventional diuretics should not be changed. If the dose of tolvaptan needs to be reduced before completion of 3-day administration at the same dose, it should be administered at the reduced dose for 3 days. If the dose of tolvaptan needs to be further reduced after dose reduction to the next lower dose, the subject will be judged to have a problem with tolerability to tolvaptan and should be withdrawn from the trial.

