## **5.7 Definition of Evaluation Dose**

Of the doses administered as specified in [Section 3.2.2](#) and [Section 3.2.3](#), the dose meeting the following criteria is defined as an evaluation dose.

- 1) If sufficient increase in urine volume was obtained during the course of dose escalation, or if the dose was increased to 0.5 mg/kg/day because sufficient increase in urine volume was not obtained:
  - If the dose was not subsequently reduced, then that dose
  - If the dose was reduced without having been administered for 3 days, then the reduced dose
  - If the dose was reduced after having been administered for 3 days, then the dose before reduction

- 2) If IMP administration was discontinued before sufficient increase in urine volume was obtained during the course of dose increase:
  - The dose at final IMP administration

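### Excessive aquaresis is a reason for an optional one-step dose reduction in Protocol 3.2.1 and 3.2.3 but, as worded, a reason to stop treatment in 3.8.3.1 item 6, and nothing separates the two rules

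*Protocol*

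**What the plan says.** Three protocol passages deal with excessive aquaresis.

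- **Protocol 3.2.1:** "If the investigator or subinvestigator judges that there are an excessive aquaresis or safety concerns of subjects, the dose may be reduced".
- **Protocol 3.2.3:** "If symptoms associated with excessive aquaresis such as persistent sensation of thirst, dehydration, and hypernatremia are observed", or if there are other safety concerns, then "at a discretion of the investigator or subinvestigator, the dose may be reduced only to the next lower dose". If 3 days at one dose had not been completed, the reduced dose is given for 3 days. Withdrawal appears only at the end: "If the dose of tolvaptan needs to be further reduced after dose reduction to the next lower dose", the child is taken not to tolerate the drug and leaves the trial.
- **Protocol 3.8.3.1:** the lead-in calls for stopping the drug and doing the withdrawal examination in each of 13 listed cases. Item 6 is "Excessive aquaresis is observed, or dose reduction to" two or more steps lower is needed on safety grounds.

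SAP 3.2.1 and 3.2.3 repeat the reduction rules; the SAP does not reproduce the stopping list. For the evaluation dose, SAP 5.7 (like Protocol 7.4) says: "If the dose was reduced without having been administered for 3 days, then the reduced dose". SAP 7.6 tabulates serious deviations, and one class is for children who met a withdrawal criterion and were kept on treatment.

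**The concern.** Take a child with excessive aquaresis for whom one step down would be enough. Under 3.2.1 and 3.2.3 the investigator may reduce the dose and continue. Under item 6, read as punctuated, treatment should stop. Both cannot be followed. Followed literally, item 6 would also cancel the reduction pathway for its own main trigger.

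Two things are at stake. The first is that identical children may be handled differently for safety. The second is the analysis: the primary objective includes finding the dose and regimen, and both efficacy and adverse events are tabulated by evaluation dose, which depends on whether the child was reduced or stopped. With 60 children planned at about 30 sites, or about 60/30 = 2 per site, most sites would meet the question rarely and without an established local practice.

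**Working it through.** No figure in the plan bears on this, so the check compares texts and follows one dosing history through the definitions.

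**Step 1: triggers.** Protocol 3.2.3 speaks of symptoms associated with excessive aquaresis. Protocol 3.2.1 and item 6 both name excessive aquaresis itself. The 3.2.1 wording alone therefore gives the same trigger as item 6.

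**Step 2: actions.** Protocol 3.2.1 and 3.2.3: optional reduction, one step, treatment continues. Item 6: discontinuation. In item 6 the two-step condition follows an *or*, so grammatically it does not qualify the first half.

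**Step 3: search for text that reconciles them.** Protocol 3.2.3, 3.2.4, 3.7.1.5, 7.4 and 3.8.3.1, and SAP 3.2.1, 3.2.3, 5.7 and 7.6, give no definition or grade of excessive aquaresis and no order of precedence. Protocol 3.2.3 and 3.8.3.1 do not refer to each other. The remark in 3.8.3.1 about reviewing the circumstances is tied to recording the date and reason; it does not clearly make stopping optional.

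**Step 4: one history, two readings.** Under Protocol 3.2.2 a child who keeps escalating receives 0.05 mg/kg/day on Days 1-2, 0.15 on Days 3-4 and 0.3 from Day 5. Suppose excessive aquaresis is judged present on Day 5, after one day at 0.3. I count the 3 reduced days from the reduction, as 3.2.3 implies: Days 6, 7 and 8, with the endpoint weight on Day 8 + 1 = Day 9.

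| | Reduced (3.2.1, 3.2.3) | Stopped (3.8.3.1 item 6) |
|---|---|---|
| Evaluation dose (Protocol 7.4, SAP 5.7) | 0.15 | 0.3 |
| Completer (Protocol 3.10) | yes, 3 days at the evaluation dose | no, 1 day |
| Endpoint weight (Protocol 7.3, SAP 5.6) | Day 9 | last available, for example at the withdrawal examination |
| Urine volume compared with baseline | mean of Days 6-8 | mean to discontinuation (Protocol 3.5.1) or over Day 5 only (SAP 6.1) |
| Dose row for efficacy and adverse events (Protocol 7.5 and 7.7.1, SAP 8.3 and 9.2) | 0.15 | 0.3 |
| Serious deviation under SAP 7.6 | possible, if item 6 is taken literally | no |

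**Step 5: the primary percentage.** It is pooled over evaluation doses, so moving from the 0.3 to the 0.15 row does not by itself change response. Response can change only because the weight is taken at a different time and the urine mean covers different days. That is possible for an individual child; the example does not show that it happens.

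**The case against.** The strongest reply is that item 6 has a natural harmonised reading. It names the same two triggers as 3.2.1 and 3.2.3, aquaresis and safety concerns, next to a reduction of two or more steps, and 3.2.3 withdraws a child who needs more than one step. On that view item 6 is the stopping-list counterpart of that sentence, and the comma and *or* may come from translation, since the protocol is marked as one. The rest of the plan leans the same way: one-step reduction has its own visit schedule (Protocol 3.7.1.5), its own evaluation-dose rule and a disposition count (SAP 7.1).

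This stands as a plausible account of intent. It does not remove the conflict, because the current text does not say it. Nor can a site safely treat the first half of item 6 as a slip: at 0.05 mg/kg/day there is no lower step, so that clause could have a purpose of its own.

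Two stronger inferences are not supported.

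- **Scale.** A reader might take the adult thirst rates in Protocol 2.2 as the share of children affected. They count any thirst, not excessive aquaresis: 21.4%, 27.3% and 53.6% at 15, 30 and 45 mg/day, against 10.3% on placebo. The top figure comes from a dose equated to 0.75 mg/kg/day, above this trial's limits of 0.5 mg/kg/day and 15 mg/day.
- **Primary result.** A reader might infer that the two readings give different primary outcomes. Under either one the child can be in the full analysis set and is scored on the doses actually given. A changed responder status is possible but not demonstrated.

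**Conclusion.** The point holds as an internal contradiction in a safety rule. For a child with excessive aquaresis in whom one step down would suffice, Protocol 3.2.1 and 3.2.3 permit reduction and 3.8.3.1 item 6, as worded, calls for discontinuation. This rests on reading item 6 as punctuated; the source-language text is not available to check. The documents do not establish that the sponsor meant every case of excessive aquaresis to end treatment.

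The effects on the evaluation dose, completer status, timing of the weight, urine window, dose row and deviation class follow directly from the definitions. An effect on responder status is only possible. The documents give no rate of aquaresis-triggered reduction in children, so the number affected is unknown; the contradiction does not depend on it.

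It is also separate from the sodium criteria. Protocol 3.2.3 lists hypernatremia among reasons for reduction while item 10 stops treatment above 145 mEq/L, but settling that would leave thirst or dehydration with normal sodium unresolved. The point should be corrected, at modest cost.

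**What to change.** Reconcile Protocol 3.2.1, 3.2.3 and 3.8.3.1 item 6 so that one consistent rule applies to excessive aquaresis, with cross-references between the sections. Which rule that is, and how any distinction between reduction and discontinuation is drawn, is for the sponsor's clinicians.

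Then align SAP 3.2.1 and 3.2.3 with the settled wording, and state in SAP 7.6 how a child reduced under 3.2.3 is treated, so that a compliant reduction is not reported as a failure to withdraw.

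The cost is a wording clarification in the protocol and matching edits in the SAP. No new CRF field is needed: the reason for dose reduction (Protocol 3.2.1) and the date and reason for discontinuation (Protocol 3.8.3.1) are already recorded there.
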